### **6.4.3 Exploratory Efficacy Endpoints**

*Primary and secondary efficacy endpoints (OS, CR, ORR, HSCT, EFS, and DOR) in the all-patient population, as well as OS and CR in the subpopulation of FLT3, IDH1, and IDH2, will be analyzed.*

*The following endpoints will be assessed in the all-patient and TP53 WT populations: CR and ORR over entire treatment period; EFS; and HSCT in patients with OR (CR/CRp/CRi) and all patients. CR over entire treatment period will also be assessed in the subpopulation of FLT3, IDH1, and IDH2.*

*Biomarker analyses are described in Section 6.8.*

## **6.5 SENSITIVITY ANALYSES**

The following sensitivity analyses for OS will be performed in the TP53 WT population:

- An unstratified log-rank test.
- To assess the relevance of HSCT against other long-term effects, OS will be alternatively defined with censoring at date of HSCT and analyzed using the same methods as for the primary endpoint.
- *Discontinuation of assessments or patient lost to follow up considered as an event*

## 6.6 SAFETY ANALYSES

All safety analyses will be based on *both the TP53 WT population (defined here as TP53 WT patients who have received any study medication at least once) and the complete safety analysis population (defined as all patients who have received any study medication at least once)*, and patients will be analyzed according to the treatment received (patients receiving idasanutlin at least once will be analyzed in the idasanutlin arm). Safety analyses will include, but not be limited to, incidence rates for adverse events including mortality, adverse event severity, seriousness, and adverse events leading to discontinuation. In addition, abnormalities of clinical laboratory tests and vital signs assessed during the study treatment period and post-treatment follow-up will be assessed. Exposure to study medication will be summarized by total duration of study medication, number of cycles started and cumulative dose using descriptive statistics.

This trial is designed to allow for early termination or a modification of the protocol for safety concerns or lack of efficacy, based on the advice of an iDMC. The iDMC will be incorporated into the study to review safety data on a regular basis, including adverse events of special interest. Both the Sponsor and the iDMC can request ad hoc iDMC meetings if potential safety concerns arise. Following each meeting, the iDMC will recommend to the Sponsor whether the study should continue according to the protocol or may suggest changes to the protocol based on the outcome of the data review. In exceptional cases, the iDMC may recommend stopping the study or closing a treatment arm as a result of safety reasons. The iDMC will also perform a safety review at the preplanned interim analyses for futility and efficacy.

## 6.7 ELECTROCARDIOGRAMS

Incidence of clinically significant ECG abnormalities will be reported in patient listings and change from baseline summarized in tables by treatment arm. ECG QT and QTcF intervals will be summarized by descriptive statistics.

## 6.8 PHARMACODYNAMIC AND BIOMARKER ANALYSES

The following pharmacodynamic parameters will be presented by listings and descriptive summary statistics.

- Blood samples analyzed for MIC-1
- Analysis of *TP53*, *FLT3*, *IDH1*, and *IDH2* mutation status
- *MDM2* protein expression level in AML blasts
- A 4-gene signature (including *MDM2* gene expression)
- *MRD*

## 6.9 PHARMACOKINETIC ANALYSES

Key PK parameter values (CL/F and Vd/F) of idasanutlin and cytarabine (CL and Vd) will be estimated using a popPK approach. The influence of covariates such as gender, race/ethnicity, weight, hematological parameters at baseline, renal/hepatic impairment, and degree of underlying disease will be investigated. Other PK parameters such as  $C_{max}$ ,  $C_{trough}$ ,  $AUC_{0-\tau}$ ,  $AUC_{0-24h}$ , and  $t_{1/2}$  will be derived from the individual post hoc predictions. Details of the population analysis will be described in the Modeling and Simulation Analysis Plan. Results of this analysis will be reported separately.

If appropriate, an exploratory PK/pharmacodynamic analysis may be performed post hoc. The primary focus will be exploration of the relationship between measures of exposure to idasanutlin in combination with cytarabine ( $C_{max}$ ,  $C_{trough}$ , and  $AUC_{0-24h}$ ) and ECG, drug-related adverse effects as well as clinical efficacy parameters.

## 6.10 PATIENT-REPORTED OUTCOME ANALYSES

Scoring for the EORTC QLQ-C30 questionnaire will be based on the scoring manual. Consistent with the user manual, prorated scores will be computed for a subscale if more than 50% of the constituent items have been completed for that subscale. For subscales with less than 50% of the items completed, the subscale will be considered as missing.

Summary statistics of the EORTC QLQ-C30 scales and their changes from baseline will be calculated at each assessment timepoint for both study arms. Analysis details of these PROs will be provided in the Statistical Analysis Plan.

Health utility scores, as assessed by the EQ-5D-5L, will be evaluated for patients with a baseline assessment and at least one post-baseline EQ-5D-5L assessment that generate a score. Scores at baseline and change from baseline scores for each timepoint will be quantified using descriptive statistics. The results will be used for more complete health economic data analysis.

## 6.11 INTERIM ANALYSES

### 6.11.1 *Futility*

A non-binding interim analysis for safety and futility will be performed by an iDMC after 120 patients with *TP53* WT have been enrolled and assessed for response. For the purposes of the *futility* interim analysis, CR is defined as confirmed CR (see definition in Section 3.4.1). Sponsor personnel will not have access to by-arm efficacy and safety summaries prior to the formal reporting of study results. The iDMC may recommend stopping the study for futility if:

- the observed odds ratio for CR in the cytarabine and idasanutlin arm versus the cytarabine and placebo arm in the population of patients WT for *TP53*, is  $< 2.0$ ,

- or the observed odds ratio for CR in the cytarabine and idasanutlin arm versus the cytarabine and placebo arm in the population of patients WT for *TP53*, is  $< 2.5$  and the hazard ratio for EFS  $> 1$ .

To compute stopping probabilities for the *futility* interim analysis, the following additional assumptions are made within *TP53* WT patients and the simulation model is extended accordingly:

- Median OS for non-responders in cytarabine arm is 5.1 months
- Median OS for responders, but short-term survivors in cytarabine arm is 7.5 months
- EFS follows an exponential distribution
- Median EFS times for non-responders and CR short-term responders is assumed to be shorter by a factor 2.5 compared to OS in these same subpopulations
- The correlation between uncensored EFS and OS times is 0.5
- Hazard ratio for a comparison of idasanutlin+cytarabine versus cytarabine +placebo in both non-responders and short-term responders is 0.8

Using these assumptions, we expect 63 EFS events at the *futility* interim analysis under the alternative hypothesis. The probability of early stopping due to futility is 89.9% if the null hypothesis of equal OS survival functions is true and 31.9% if the alternative assumption of an increase in median OS from 6 to 9 months is true.

The analysis in both the *TP53* WT population and in the overall population will be provided to the iDMC.

The iDMC may recommend stopping the study for safety at the *futility* interim analysis if any of the following criteria are met (note: early death is defined as any death within the first 30 days after randomization):

- The proportion of GI toxicity (nausea, vomiting, diarrhea) events in the experimental arm (idasanutlin + cytarabine): Grade 3  $> 40\%$  or Grade 4  $> 15\%$
- The proportion of early deaths in the experimental arm (idasanutlin + cytarabine) is  $\geq 10$  percentage points greater than in the control arm (cytarabine + placebo)
- $> 20\%$  of early deaths overall in the treatment arm

More details on the interim analysis are provided in the iDMC charter.

### **6.11.2**      *Efficacy*

*An interim analysis for efficacy on OS is planned to be conducted by iDMC. The efficacy interim analysis will be conducted when 80% of the OS events have occurred (i.e., approximately 220 events). At this time, it is anticipated that all patients will have been enrolled (see Section 6.1).*

*For the interim efficacy analysis of OS, the significance level will be determined using the O'Brien-Fleming alpha-spending function with overall type I error rate at 0.05 level. At the time of the interim efficacy analysis, it is expected that 80% of the OS events will have occurred, corresponding to an alpha spending of 0.025 for the interim and 0.043 for the final OS analysis leading to a power of 83% for the final analysis.*

*The iDMC will test OS for efficacy and check if there is a significant difference (alpha level 0.025 or as assessed based on actual number of OS events) in OS in favor of the experimental arm.*

*Accompanying this interim efficacy analysis, a non-binding additional futility assessment will be performed and the iDMC may recommend stopping the study for futility if the hazard ratio on OS is greater than or equal to one.*

*Further details of the interim analyses will be described in the iDMC Charter and Statistical Analysis Plan.*

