## **6. STATISTICAL CONSIDERATIONS AND ANALYSIS PLAN**

### **6.1 DETERMINATION OF SAMPLE SIZE**

A mechanistic simulation model *was* used to determine the sample size in this event-driven study, based on the following global assumptions:

- Final analysis for OS in patients with *TP53* WT disease based on two-sided log-rank test at 0.05 level of significance
- 85% power to detect an OS hazard ratio for idasanutlin + cytarabine versus cytarabine + placebo of 0.67 in patients with *TP53* WT disease, corresponding to an improvement in median OS from 6 to 9 months (50%)
- Proportion of long term survivors of 8.0% in the cytarabine + placebo arm and 16.1% in the idasanutlin + cytarabine arm

To compute the necessary number of events, we *simulated* OS times based on the following assumptions:

- All simulated OS times for patients not considered long-term survivors are exponentially distributed
- Probability of being a complete responder in the cytarabine + placebo arm is 0.16
- Probability of being a complete responder in the idasanutlin + cytarabine arm is 0.323, implying an odds ratio for CR comparing the idasanutlin + cytarabine versus the cytarabine + placebo arm of 2.5
- Probability for a complete responder to be a long-term survivor is 0.5 in either arm

- An annual dropout rate of 5% (every effort will be made to contact patients for survival information in case of study withdrawal or loss to follow-up)

To have the targeted 85% power, 275 events *in patients with TP53 WT disease* are required. The minimum detectable hazard ratio in a 2:1 randomized trial corresponding to 275 events and a significance level of 0.05 amounts to 0.78, corresponding to a minimal detectable median improvement from 6 to 7.7 months assuming exponentiality.

All patients, *regardless of TP53 mutation status*, will be randomized to this study. Assuming 85% of patients will have TP53 WT disease and 15% will have TP53 mutant disease, approximately 440 patients will be enrolled over approximately 29 months, corresponding to an estimated number of 374 patients *with TP53 WT disease*.

*In Version 6 of the protocol, an interim analysis for efficacy on OS of TP53 WT patients was added. The sample size assumptions above remain unchanged other than the recruitment time (now estimated at 41 months). The interim analysis will occur at an information fraction of 80%, providing a maximum power of 83% for the final OS analysis (see Section 6.11.2).*

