### 2.3 DETERMINATION OF SAMPLE SIZE

A mechanistic simulation model was used to determine sample size based on the following assumptions:

- Final analysis on OS in patients with *TP53* wild type (WT) using a 2-sided log-rank test at the 5% significance level
- 85% power to detect an OS HR (HR) of 0.67 for idasanutlin + cytarabine versus placebo + cytarabine in patients with *TP53* WT, corresponding to a 33% risk reduction of death, corresponding to an improvement in median OS from 6 months to 9 months (50%)
- Proportions of long-term survivors of 8.0% in the placebo + cytarabine treatment arm and 16.1% in the idasanutlin + cytarabine treatment arm

To compute the necessary number of events, OS times were simulated based on the following assumptions:

- All simulated OS times for patients not considered to be long-term survivors were exponentially distributed.
- Probability of being a CR in the placebo + cytarabine treatment arm was 0.16.
- Probability of being a CR in the idasanutlin + cytarabine treatment arm was 0.323, implying an odds ratio for CR of 2.5 for idasanutlin + cytarabine versus placebo + cytarabine.
- Probability for a CR to be a long-term survivor was 0.5 in either treatment arm.
- An annual dropout rate was 5%.

Based on these assumptions, approximately 275 OS events in patients with *TP53* WT are required to provide 85% power for the primary analysis. The minimum detectable OS HR in this study is 0.78, assuming 275 OS events and a significance level of 5%, which corresponds to a minimal detectable median improvement from 6 to 7.7 months assuming exponentiality.

All patients will be randomized in this study. Assuming 85% of patients will have *TP53* WT and 15% will have *TP53* mutant disease, approximately 440 patients will be enrolled over approximately 29 months, corresponding to an estimated number of 374 patients with *TP53* WT.

In Version 6 of the protocol, an interim analysis for efficacy on OS of *TP53* WT patients was added. The sample size assumptions above remain unchanged other than the recruitment time (now estimated as 41 months). The interim analysis will occur at an information-fraction of 80% providing a power of 83% for the final OS analysis (see section 4.11.3).

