#### **4.11.3 Efficacy Interim Analysis**

At the time of the efficacy interim analysis (on OS) that will be conducted when 80% of the events have occurred (i.e., approximately 220 events), it is

anticipated that all patients have been enrolled. OS will be tested at the significance level determined using the O'Brien-Fleming alpha-spending function so the overall Type I error rate will be maintained at the 0.05 level. With 80% information, the alpha spending is 0.024.

The iDMC may recommend unblinding the study for efficacy if there is a significant difference in OS in favor of the experimental arm (alpha level 0.024 or as assessed based on actual number of OS events).

Accompanying this interim efficacy analysis, a non-binding additional futility assessment will be performed and the iDMC may recommend stopping the study for futility if the hazard ratio on overall survival is greater than or equal to one.

Further details about the interim analyses will be described in the iDMC Charter.

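### The significance levels for the OS test disagree: 0.025 and 0.024 at the interim, and a 4% cap in SAP 4.4.1, where the named spending function gives 0.0244 and 0.0429

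*Protocol*

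**What the plan says.** **Spending rule and timing.** Protocol 6.11.2 names an "O'Brien-Fleming alpha-spending function with overall type I error rate at 0.05 level" and places the interim "when 80% of the OS events have occurred (i.e., approximately 220 events"). SAP 4.11.3 uses the same function, the same overall 0.05 and the same 220 deaths.

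**Levels.**
- Protocol 6.11.2 describes the design as "corresponding to an alpha spending of 0.025 for the interim and 0.043 for the final OS analysis leading to a power of 83" per cent, and gives the interim decision level as "alpha level 0.025 or as assessed based on actual number of OS events". The Protocol synopsis says the same, and SAP Appendix 1 reprints that synopsis.
- SAP 4.11.3 gives "alpha level 0.024 or as assessed based on actual number of OS events".
- SAP 4.4.1 says that the two-sided stratified log-rank test of OS is run at an overall level of at most 4%.
- SAP 4.4.2 controls the overall type I error across OS and the secondary endpoints at 5%.

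**Planning figures.** Protocol 6.1 still lists "Final analysis for OS in patients with *TP53* WT disease based on two-sided log-rank test at 0.05 level of significance". SAP 2.3 states "The minimum detectable OS HR in this study is 0.78, assuming 275 OS events and a significance level of 5" per cent, equated with a median gain from 6 to 7.7 months; Protocol 6.1 gives the same figure. Protocol 6.1 then says that the interim comes at 80% information, "providing a maximum power of 83% for the final OS analysis". SAP 2.3 gives the same 83% without the word maximum.

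**The concern.** The interim OS analysis can lead to early unblinding of a Phase III trial, so its threshold should be one number fixed in advance. As printed, an interim p-value between 0.024 and 0.025 is significant under the Protocol and not under the SAP, and the SAP contradicts itself between 4.11.3 and Appendix 1. For the final analysis a reader can find 0.05 (Protocol 6.1), 0.043 (Protocol 6.11.2) or 4% (SAP 4.4.1). The pairs that can be assembled from these do not all spend 0.05.

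The minimum detectable HR has a related problem. It was computed for one test at 0.05, and with an efficacy interim in place OS is no longer tested at that level at either look.

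**Working it through.** **Inputs.** Overall two-sided level 0.05 with O'Brien-Fleming spending, and interim at 220 of 275 deaths, so t = 220/275 = 0.80 (Protocol 6.11.2, SAP 4.11.3). Randomization 2:1 (Protocol 4.2). Control median 6 months (Protocol 6.1).

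**1. Interim level.** Two-sided spend = 4[1 − Φ(z/√t)] with z = 2.2414, the upper 1.25% point of the normal distribution. 2.2414/√0.8 = 2.506, so the spend is 0.0244 (critical value 2.250). At the first look the amount spent and the nominal level are the same number. SAP 4.11.3 is therefore the correctly rounded value. Two other forms were tried: the classic O'Brien-Fleming boundary gives 0.0238, and the one-term form 2 − 2Φ(1.96/√t) gives 0.0284. Neither gives 0.025.

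**2. Final level.** With correlation √0.8 between the two statistics, the final critical value that brings the total to 0.05 is 2.025, a two-sided level of 0.0429. The Protocol's 0.043 is reproduced.

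**3. What each printed pair spends** (two-sided, same bivariate normal):

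| Interim | Final | Overall |
|---|---|---|
| 0.0244 | 0.0429 | 0.0500 |
| 0.024 | 0.043 | 0.0499 |
| 0.025 | 0.043 | 0.0504 |
| 0.024 | 0.04 | 0.0474 |

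If 0.025 were kept at the interim, the final level would have to fall to 0.0425.

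**4. Could 4% be the overall level?** Spending 0.04 instead of 0.05 changes z to 2.3263. Then 2.3263/√0.8 = 2.601, and the interim level is 0.0186. Neither 0.024 nor 0.025 goes with an overall 4%.

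**5. Minimum detectable HR** = exp(−z/√(D × 2/9)), where D is the number of deaths.
- 275 deaths at 0.05: √61.11 = 7.817; exp(−1.960/7.817) = 0.778; 6/0.778 = 7.7 months. The plan's figure is reproduced.
- 275 deaths at 0.0429: exp(−2.025/7.817) = 0.772; 6/0.772 = 7.8 months.
- 220 deaths at 0.0244: √48.89 = 6.992; exp(−2.250/6.992) = 0.725; 6/0.725 = 8.3 months.

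As an illustration, an observed HR of 0.775 at 275 deaths gives z = 0.2549 × 7.817 = 1.993 and p = 0.046. It lies inside the stated 0.78 but misses the final level.

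**6. Power.** The plan's own mixture model was simulated with 10,000 runs: 374 TP53 WT patients, CR 0.16 and 0.323, half of complete responders long-term survivors, control medians 5.1 and 7.5 months, HR 0.8 in the remaining patients, and 5% annual dropout. Uniform accrual over 29 or 41 months is an assumption. Its medians are 5.96 and 8.97 months.
- Single test at 0.05: 85.3–85.6%, so the planned 85% is reproduced.
- Final test alone at 0.043: 83.7–84.3%.
- Either look: 84.6–85.1%.

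A normal approximation calibrated to 85% (drift 1.960 + 1.036 = 2.996) gives Φ(2.996 − 2.025) = 83.4% for the final test and 84.3% across both looks.

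**The case against.** The strongest reply is that the printed interim level is only an illustration. Both documents define the level by the spending function, and both allow it to be recalculated from the actual deaths. The same formula gives 0.0240 at 219 deaths, 0.0244 at 220, 0.0248 at 221 and 0.0252 at 222, so the two printed values lie within about two and a half deaths of each other. The excess error from 0.025 with 0.043 is 0.0004. The synopsis in SAP Appendix 1 is a reprint, not an independent error. All of this stands, and it makes the practical effect small. It does not remove the conflict: the recalculation is joined to the printed number by the word or, and at exactly 220 deaths recalculating contradicts the Protocol's 0.025. Nor does it explain the 4%.

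Three stronger readings are tempting, and the documents do not support them.
- **That 83% is wrong.** It is labelled as power for the final OS analysis and reproduces as that. A plain proportional-hazards formula at HR 0.67 and 275 deaths gives 87.9% at 0.05 and would suggest an error, but the plan assumes a fraction of long-term survivors, which that formula ignores.
- **That 0.78 is an arithmetic error.** It is correct for the 0.05 stated beside it. It was simply not updated, and the difference is 0.006 on the HR scale under an unstratified approximation.
- **That the 95% CI for the HR is a mistake because it can exclude 1 when the test fails.** A 95% CI for estimation beside a group-sequential test is conventional, and neither document defines rejection through the interval.

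**Conclusion.** The levels are inconsistent as written. The 0.025 in Protocol 6.11.2 and both synopses is not what the named function gives at 80% information; the value is 0.0244. The larger conflict is the 4% in SAP 4.4.1, which matches neither the overall 0.05 nor the final 0.0429. It may be the final level rounded to a whole percent and mislabelled as overall, but the SAP does not say so.

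The consequences for error are small in both directions: 0.0504 for the Protocol's pair, 0.0474 if the SAP's 0.024 is followed by a final test at 4%. A reader might infer a material inflation of type I error, and the figures do not show one. The minimum detectable HR is out of date by one unit in the second decimal. The 83% stands, but calling it a maximum is misleading, because power across both looks is slightly higher, about 84–85%.

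These results assume the interim at exactly 220 of 275 deaths, the usual normal approximation to the log-rank test, and 2:1 allocation of information. The iDMC charter was not available, so which level it carries is unknown.

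**What to change.** 1. State one set of levels wherever they appear: overall two-sided 0.05, interim 0.0244, final 0.0429, with both recalculated from the actual number of deaths. Say that the recalculated level governs and that the printed values are for 220 and 275 deaths.
2. Replace 0.025 in Protocol 6.11.2 and in both synopses, bring SAP 4.11.3 to the same precision, and replace the 4% in SAP 4.4.1. Check that the iDMC charter agrees.
3. Restate the minimum detectable HR as 0.77 (6 to 7.8 months) at the final level in Protocol 6.1, SAP 2.3 and both synopses. If 0.78 is kept, label it as a single test at 0.05 without an interim.
4. Keep the 83%, and drop the word maximum in Protocol 6.1 and the matching synopsis text. Overall power of about 84–85% may be added beside it.

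The cost is wording only. No change to the design, sample size or number of events is needed, and the stated detectable effect becomes slightly less favourable.
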